### **3.8.4. Clinical Laboratory Evaluation**

The clinical laboratory parameters will be analyzed using the Safety Analysis Set by cohort and overall.

Laboratory values will be assigned toxicity grades when available using the NCI CTCAE version 5.0. Directional shifts in laboratory toxicity grades from baseline to post-baseline highest grade will be tabulated. For analytes without a toxicity grading scale, shift tables will present directional shifts from baseline to above or below the laboratory standard normal range.

All clinical laboratory values will be presented in patient listings. Out of normal range values will be flagged.

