7.3.2.2. Laboratory Values

Laboratory values will be assigned toxicity grades when available using the NCI CTCAE, version 5.0 or later. Directional shifts in laboratory toxicity grades (comparing baseline grade with worst post-baseline grade) will be analyzed using standard shift tables, presenting number and proportion of patients and their maximum grade shift. For analytes without a toxicity grading scale, the shift table will present directional shifts from baseline to above or below the laboratory standard normal range using the maximum increase and/or decrease observed throughout the course of treatment/observation. Descriptive statistics for the actual values of clinical laboratory parameters (and/or change from baseline in clinical laboratory parameters) and other safety parameters as deemed appropriate will be presented for all scheduled measurements over time. Mean laboratory values over time will be presented for key laboratory parameters.

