Report and record all SAEs to the Sponsor or designee within 24 hours following the Investigator's knowledge of the events, as indicated in Appendix G. The Investigator will submit any updated SAE data to the Sponsor within 24 hours of their being available.

Non-serious AESIs should be reported in the same manner as reporting of SAEs. In addition, for both serious and non-serious AESIs, the appropriate targeted questionnaires should be submitted to the Sponsor with the SAE report or as soon as possible.

If the Investigator learns of any SAE and/or AESI, including a death, at any time after a patient has been discharged from the study, and he/she considers the event to be reasonably related to the study intervention or study participation, the Investigator must promptly notify the Sponsor.

8.1.2. Method of Detecting Adverse Events, Adverse Events of Special Interests, and Serious Adverse Events

The method of recording, evaluating, and assessing causality of AEs, AESIs, and SAEs and the procedures for completing and transmitting SAE and non-serious AESI reports are provided in Appendix G.

Care will be taken not to introduce bias when detecting AEs, AESIs, and/or SAEs. Open-ended and nonleading verbal questioning of the patient or the patient's parent/legal guardian is the preferred method to inquire about AE occurrences.

8.1.3. Follow-up of Adverse Events, Adverse Events of Special Interests, and Serious Adverse Events

After the initial AE/SAE report, the Investigator is required to proactively follow each patient at subsequent visits/contacts. All SAEs will be followed until resolution, stabilization, the event is otherwise explained, or the patient is lost to follow-up. Further information on follow-up procedures is provided in Appendix G.

Non-serious AESIs should be followed-up in the same manner as SAEs.

If a patient begins a new anticancer therapy prior to 30 days post study drug EOT, the AE reporting period for non-SAEs and SAE/AESIs not related to study drug ends at the time the new treatment is started.

8.1.4. Regulatory Reporting Requirements for Any SAEs and Non-Serious AESIs Occurring During this Study Must Be Reported as Follows:

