### **3.1.6. Handling of Missing/Incomplete Date/Time**

All analyses of AEs will be based on the principle of treatment emergence. Treatment emergent adverse events (TEAEs) are defined as new or worsening adverse events occurring on or after the first administration of study treatment until 30 days after the last dose of study treatment or before the start of subsequent therapy, whichever comes first. For missing or incomplete AE start dates, the following criteria will be used to determine whether an AE is treatment emergent:

Missing AE start day:

- If the partial date contains a different month or year from the date of first study dose, then impute it as the first day of the month.
- If it contains the same month and year as the date of first dose, then impute it as date of first dose.

Missing AE start day and month:

- If the partial date contains a different year from the date of first dose, then impute the missing day and month as Jan 01.
- If it contains the same year as the date of first dose, then impute the missing day and month as day and month of first dose.

Completely missing AE date:

- Missing date will not be imputed and AE is considered treatment emergent.

A medication will be considered concomitant if it is taken on or after the date of first dose of study treatment. In order to determine whether a medication with an incomplete or missing start or end date is concomitant, the following criteria will be used:

- If the start date of a medication is on or after the first dose date and the stop date of the medication is missing, that medication is considered concomitant.
- If the start date of a medication is missing and the stop date of that medication falls on or after the first dose date, that medication will be considered concomitant.
- If the start date of a medication is prior to the first dose date and the stop date of the medication is missing, that medication is considered not concomitant.
- If the start date of a medication is missing and the stop date of the medication is prior to the first dose date, that medication is considered not concomitant.
- If both the start and stop dates of a particular medication are missing, that medication will be considered not concomitant.

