### **3.1.7.2. Analysis Visit Windows**

No analysis visit windows will be identified for the safety summaries. Visit-based data summaries will be based on the protocol scheduled visits.

If more than one assessment is available for a given post-baseline visit, the worst observation will be selected for visit-based summaries.

Any data relating to unscheduled visits will not be assigned to a particular visit or time point. However, the following exceptions will be made:

- Unscheduled visit prior to first dose of study drug may be included in the calculation of baseline value if applicable.
- Unscheduled visits after the first dose of study drug will be considered in summaries for the extreme post-baseline value.

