#### **3.3.3.1. Adverse Events**

All AEs will be coded using the Medical Dictionary of Regulatory Activities (MedDRA) Version 24.0 or later and will be classified by MedDRA System Organ Class (SOC) and Preferred Term (PT). Analyses of AEs will be based on the principle of treatment emergence. An AE is considered to be treatment-emergent if it has a start date/time on or after the date/time of first dose of study drug up to 30 days after the last dose of study treatment and before the start of subsequent therapy, whichever comes earlier.

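### The worst post-baseline laboratory grade in SAP 3.8.4 has no end date, unlike the SAP's adverse event window, so any value recorded after new anticancer therapy would enter the shift table.

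*SAP*

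**What the plan says.** **Laboratory rule.** SAP 3.8.4 states: "Directional shifts in laboratory toxicity grades from baseline to post-baseline highest grade will be tabulated". Analytes without a grading scale get shifts to above or below the normal range. The tables use the Safety Analysis Set, by cohort and overall.

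**Visits.** SAP 3.1.7.2 says "No analysis visit windows will be identified for the safety summaries". Its second exception for unscheduled data is: "Unscheduled visits after the first dose of study drug will be considered in summaries for the extreme post-baseline value". That sentence has a starting point and no finishing point.

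**Protocol counterpart.** Protocol 7.3.2.2 builds the shift tables by "comparing baseline grade with worst post-baseline grade". For ungraded analytes it does so "using the maximum increase and/or decrease observed throughout the course of treatment/observation".

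**Adverse events.** SAP 3.3.3.1 counts an event as treatment-emergent from first dose "up to 30 days after the last dose of study treatment and before the start of subsequent therapy, whichever comes earlier". SAP 3.1.6 gives the same end: "until 30 days after the last dose of study treatment or before the start of subsequent therapy, whichever comes first".

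**New therapy.** Protocol 8.1.3 provides for a patient who starts another treatment early, with a rule that opens "If a patient begins a new anticancer therapy prior to 30 days post study drug EOT". Collection of non-serious events, and of serious or special-interest events unrelated to study drug, then ends when the new treatment starts.

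**The concern.** The TEAE tables and the laboratory shift tables both serve the secondary safety objective and use the same patients, but they cover different periods. The TEAE window is closed so that events under the next regimen are not counted. The laboratory maximum has no such closure.

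If a patient has blood drawn after starting another regimen, a severe abnormality caused by that regimen can become the patient's worst grade in the tovorafenib shift table. The same abnormality would be absent from the TEAE tables. A reader comparing the two outputs would find a severe laboratory shift with no matching event, and no stated rule to explain it. In a single-arm study no control column shows how much of a shift table reflects later treatment.

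**Working it through.** No figure in the plan bears on this point, so the check sets the rules side by side.

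| Output | Start | End | Stops at new therapy? |
|---|---|---|---|
| TEAEs (SAP 3.1.6, 3.3.3.1) | First dose | 30 days after last dose, or subsequent therapy if earlier | Yes |
| PFS (SAP 6.3) | First dose | Censored at last evaluable assessment before new treatment | Yes |
| Laboratory shifts, graded (SAP 3.8.4; Protocol 7.3.2.2) | After baseline | None stated | No |
| Laboratory shifts, ungraded (Protocol 7.3.2.2) | After baseline | Treatment or observation period | No |
| Unscheduled values in extremes (SAP 3.1.7.2) | First dose | None stated | No |

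**Does another passage close the laboratory window?** I found none. SAP 3.1.3 defines baseline, but nothing defines the end of post-baseline. The protocol wording for ungraded analytes reaches past treatment. After early termination, SAP 2.2.1 and 2.3.3 place the final analysis after all patients have ended the study, so an early data cut-off does not close it either.

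**How could a late value arise?** The readable text leaves two routes.
1. A draw at the end-of-treatment or safety follow-up visit, taken after new therapy has begun. Protocol 8.1.3 recognises that new therapy may start within the 30 days, and Protocol 6.24 and 6.25 put no new-therapy condition on these visits.
2. An unscheduled value entered in the database, which SAP 3.1.7.2 admits.

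**Direction.** Let G be a patient's highest grade inside the TEAE window and L the highest grade recorded after new therapy starts. If no other values fall outside the window, the shift table shows max(G, L), which is at least G. As a hypothetical case, if G = 1 and L = 4, the table shows 4. Adding values can never lower the worst grade.

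**Disagreement with the event tables.** SAP 3.3.3 has clinically significant laboratory abnormalities reported as adverse events. One that arises after new therapy is not treatment-emergent under SAP 3.3.3.1, and if non-serious it falls outside the collection period (Protocol Table 8, footnote). The value itself still counts under SAP 3.8.4.

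**Size.** The number of patients whose worst grade is altered by new therapy cannot exceed the number with a laboratory value recorded after new therapy starts. The documents do not give that number. The hematology and chemistry timing in SAP Table 2 is redacted, so the last scheduled draw cannot be read. If no such values exist, the effect is zero.

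**Would a 30-day limit cut off drug exposure?** Protocol 1.3.2 gives a mean terminal half-life of 70 hours. Thirty days is 30 × 24 = 720 hours, and 720 / 70 is about 10.3 half-lives.

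**The case against.** The strongest reply is that contamination is possible but not shown, and that stands. No readable text schedules laboratory tests in long-term follow-up. Protocol 6.26 names continued tumor assessment for patients who stop before progression, and subsequent therapies and survival status after progression, when contact may be by telephone. SAP 2.3.6 repeats the continued assessment under efficacy. A shift table also assigns no causality, so the risk is misreading rather than formal attribution.

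A second reply is that the protocol itself is open-ended. Protocol 7.3.2.2 covers the whole treatment or observation period for ungraded analytes, and the TEAE definition in Protocol 7.3.2 runs to the clinical cut-off date. The mismatch therefore comes from the SAP's narrower TEAE window. This is correct, and it means the change departs from the protocol and must be recorded. It does not justify two unaligned periods within one SAP. SAP section 4, which lists only the efficacy set, does not mention the TEAE difference either.

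A third reply is that all laboratory values are listed with out-of-range values flagged, so a late value can be traced. That limits the harm but does not correct the table. The study was also stopped early, and no decision rule uses these tables. This keeps the point modest.

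Some stronger inferences are not supported:
- **Shift tables as the only planned laboratory summary.** Protocol 7.3.2.2 also plans descriptive statistics over time and mean values for key parameters. The statement could hold only for what SAP 3.8.4 itself tabulates.
- **A safety visit fixed at 28 days or more after the final dose.** Protocol 6.25 says only when safety follow-up may be merged with the end-of-treatment visit, and it allows a telephone contact.
- **The same defect for ECG and LVEF.** SAP 3.3.3.7 and 3.3.3.8 specify no extreme-value summary for either.

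**Conclusion.** The gap is real: SAP 3.8.4, with the second exception in 3.1.7.2, sets no end of window for the worst post-baseline laboratory value, while the SAP's TEAE window has one. Any value recorded after new anticancer therapy starts would be included. It could only raise the worst grade or leave it unchanged, and it could put the shift table at odds with the adverse event tables for that patient.

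A reader might infer that toxicity from the next treatment is in fact being reported as tovorafenib toxicity, or might attach a percentage to the inflation. The documents support neither. Both need laboratory values drawn after new therapy, and the schedule that would show whether these exist is redacted. The size is unknown and may be zero. The conclusion rests on reading the stated rules literally, not on evidence that such values were collected. It is a worthwhile, inexpensive correction.

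**What to change.** - In SAP 3.8.4, and in the second exception of 3.1.7.2 as it applies to laboratory data, take the worst post-baseline value only over values after first dose up to the earlier of 30 days after last dose and the day before subsequent anticancer therapy starts.
- Keep later values in the patient listing, with a flag.
- Record the change in SAP section 4 as a departure from the treatment or observation period in Protocol 7.3.2.2.

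The cost is a short text change and a date filter. The dates needed are already collected: subsequent anticancer treatment appears in Protocol 6.21 and SAP Table 2. If no late values exist, the results do not change. The one downside is that a delayed abnormality first seen after the window would appear only in the flagged listing.

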### **3.8.5. Visual Acuity**

Visual acuity assessments will be summarized at [REDACTED] timepoints by cohort and overall for all patients in the Safety Analysis Set. Descriptive statistics for right and left eye acuity values will be presented.

All visual acuity results will be included in a patient listing.

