##### **3.1.2. Reporting of Numerical Values**

Relevant descriptive statistics (n, mean, standard deviation, median, minimum, and maximum) will be calculated for continuous variables. Confidence intervals (CIs) will be provided where appropriate.

Frequencies and percentages will be presented for categorical and ordinal variables, with the frequencies reported as integers and percentages reported with one decimal place. Unless otherwise specified, the percentages will be calculated based on the total number of patients included for the analysis group. Frequencies and percentages for patients with missing data may be presented.

Means, medians, and confidence intervals will be reported to one decimal place more than the data reported on the case report form (CRF) or by the laboratory/vendor. Standard deviations will be reported to two decimal places more than the data.

A month is operationally defined to be 30.4375 days. Six months is operationally defined to be 182.625 days. One year is defined to be 365.25 days.

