#### **3.3.3.5. Ophthalmology Examination and Visual Acuity**

A baseline ophthalmology exam will be performed for all patients at [REDACTED]. If the patient has noted any visual changes, ophthalmology exam will be conducted prior to the start of each new cycle starting with [REDACTED]. If any visual changes are noted at [REDACTED] [REDACTED] visit an ophthalmology exam will be conducted. Acuity of right and left eyes will be measured in logMAR.

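### As SAP 3.3.3.5 describes it, eye exams after baseline are symptom-triggered, so the raw acuity means by timepoint in SAP 3.8.5 are not comparable across rows

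*SAP*

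**What the plan says.** SAP 3.3.3.5 sets out when eyes are examined. For the start of the study: "A baseline ophthalmology exam will be performed for all patients at" a visit whose name is redacted. During treatment: "If the patient has noted any visual changes, ophthalmology exam will be conducted prior to the start of each new cycle starting with" a redacted cycle. A third sentence covers one more redacted visit. If visual changes are noted at that "visit an ophthalmology exam will be conducted". The redactions hide the visits but not the condition. The section ends by fixing the scale: "Acuity of right and left eyes will be measured in logMAR".

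SAP 3.8.5 says acuity will be summarised at redacted "timepoints by cohort and overall for all patients in the Safety Analysis Set", and that "Descriptive statistics for right and left eye acuity values will be presented". SAP 3.1.2 defines what that means: "Relevant descriptive statistics (n, mean, standard deviation, median, minimum, and maximum) will be calculated for continuous variables".

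Three general rules also bear on the table:
- SAP 3.1.4 uses observed values without imputation unless stated otherwise.
- SAP 3.1.7.2 bases visit summaries on scheduled visits. It keeps unscheduled data out of individual timepoints, but allows them in the baseline value and in extreme post-baseline values.
- SAP 3.1.3 defines change from baseline, but 3.8.5 does not call on it.

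Sections 6.11 and 6.12 of the master protocol send the reader to the sub-protocols for the eye exam and the visual symptom assessment.

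**The concern.** The patients measured change between rows, and they change according to the outcome being measured. At baseline everyone contributes. At a later timepoint, on the text of 3.3.3.5, a patient contributes an acuity value because vision appeared to have changed. A reader who looks down the column of means would naturally take it as a time course for the treated population, which it would not be.

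This matters because visual acuity is one of the safety variables named in SAP 3.3.3, and ocular toxicity is an adverse event of special interest. Section 3.8.5 is the only planned quantitative summary of measured acuity. As written it gives neither the within-patient change nor the share of treated patients with a measured worsening.

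**Working it through.** The plan states no acuity figure, and the sample sizes in SAP Table 1 are redacted, so there is nothing to reproduce. The check has two parts: setting the sections side by side, and an illustration on assumed inputs.

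**Sections side by side**
- Baseline row: all patients (3.3.3.5), summarised over the Safety Analysis Set (3.8.5).
- Later rows: only patients with visual changes (3.3.3.5), observed values only (3.1.4), same statistics (3.1.2).
- Nothing restricts the baseline row to patients examined later, asks for a paired change in acuity, or labels later values as symptom-triggered.
- If a triggered exam is recorded as an unscheduled visit, 3.1.7.2 leaves it out of the by-timepoint rows altogether. It could enter only a summary of extreme post-baseline values, and 3.8.5 plans none.

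**What the row difference contains**

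Let B_all be the baseline mean in all patients, B_ex the baseline mean in those examined later, d_ex their mean within-patient change, d_un the mean change in unexamined patients, and p the share examined.
- Later mean minus baseline mean = (B_ex − B_all) + d_ex.
- All-patient change = p × d_ex + (1 − p) × d_un.

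Pairing removes the first bracket and leaves d_ex. It does not give the all-patient change, because d_un is not measured.

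**Illustration (every input assumed)**

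Take B_all = B_ex = 0.10 logMAR, d_ex = 0.20 and d_un = 0. The later row reads 0.10 + 0.20 = 0.30 whatever p is. The all-patient mean would be 0.10 + p × 0.20:

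| Share with visual changes (p) | Later row shown | All-patient later mean |
|---|---|---|
| 5% | 0.30 | 0.11 |
| 10% | 0.30 | 0.12 |
| 20% | 0.30 | 0.14 |
| 30% | 0.30 | 0.16 |

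A simulation on these inputs (20,000 replicates, with a baseline SD of 0.15 and a within-patient SD of 0.05 also assumed) gave observed later means of 0.298 to 0.301 and a paired change of 0.20 among those examined.

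**How many patients a later row might hold**

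Assume N patients, all still on study, each with visual changes independently with probability p. The expected number is N × p. The chance that two or fewer contribute is the sum over k = 0, 1, 2 of C(N, k) p^k (1 − p)^(N − k).

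| N (assumed) | Expected number, p = 5% to 30% | Chance of 2 or fewer at p = 10% |
|---|---|---|
| 20 | 1 to 6 | 68% |
| 40 | 2 to 12 | 22% |
| 60 | 3 to 18 | 5% |

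These are overall figures. Rows by cohort would hold fewer.

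**The case against.** The strongest reply is that the deciding text is out of view. The timepoints in 3.8.5 are redacted. In SAP Table 2 the ophthalmologic exam and the visual symptom assessment carry footnotes l and m, whose text cannot be seen, and the sub-protocol was not available. SAP 2.3.7 lists the ophthalmologic exam and visual acuity as separate items, and the logMAR sentence in 3.3.3.5 carries no condition of its own. Acuity might therefore be measured routinely at some later visit. This stands as a limit and makes the point conditional. It does not dispose of it, because no visible text describes a routine later measurement and Table 2 has no separate acuity row.

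The second reply is that the harm is contained. Under 3.1.2 each row shows its n, and 3.8.5 lists every result by patient. SAP 3.8.3 summarises ocular toxicity from treatment-emergent events over the Safety Analysis Set. No test or decision depends on this table. All of this stands, and it keeps the point small. But event terms are not measured acuity, and neither n nor a listing supplies a within-patient summary.

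A reader might go further and infer that the table will show a large false loss of vision, overstated perhaps tenfold. The documents do not support that. A tenfold ratio would come, for example, from assuming that 5 of 50 patients are examined and the other 45 are unchanged. It is only 50 / 5, the inverse of the assumed share.

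Finally, pairing does not by itself cure the selection. In the illustration the paired change is 0.20, the same as the gap between rows, against an all-patient change of 0.01 to 0.06. That is correct, and it is why paired change needs a label and a second summary with a full denominator.

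**Conclusion.** The point holds conditionally. If the unseen schedule footnote and sub-protocol contain no routine later acuity measurement, the baseline and later rows of the 3.8.5 table describe different groups. Their means should not be compared, and an apparent change could partly reflect who was examined. The size and even the direction of any distortion cannot be stated from the documents. The figures above show the mechanism on assumed inputs and do not estimate this trial.

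It would be wrong to infer that ocular harm goes unquantified, since the adverse-event summary reports ocular events with the full safety denominator. What is missing is a usable summary of measured acuity. This is a minor defect in one descriptive safety table, cheap to put right, and it does not touch the efficacy conclusions.

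**What to change.** In SAP 3.8.5:

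- (a) Replace the raw by-timepoint comparison with change from each patient's own baseline (3.1.3), per eye, in the patients examined. Show the number examined and the number on treatment at each timepoint. Add a footnote that later exams are symptom-triggered and that the change applies to examined patients only.
- (b) Add the number and percentage of the Safety Analysis Set whose worst post-baseline value, per eye, worsened from baseline by more than a logMAR threshold stated in advance. Include unscheduled exams, as 3.1.7.2 allows for extreme values. Without a threshold, ordinary test-retest variation would count as loss. State that unexamined patients are counted as having no documented worsening, and show how many were examined at least once after baseline.

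The SAP already uses a baseline-to-worst layout for laboratory grades in 3.8.4, so the programming is familiar. The cost is one re-specified table and agreement on a threshold, with no new exams. If a routine later exam does exist in the schedule or sub-protocol, reconcile 3.3.3.5 with it so that the section says so, and drop the symptom-triggered label for that visit.
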